8.2. Screening and Enrollment

The study will be explained in lay terms to each potential research participant. The potential participant will sign an informed consent form before undergoing any study procedures. Once informed consent is obtained, all screening procedures, assessments, and laboratory measures to determine participant eligibility will be conducted within a 30-day screening window. Eligible participants who meet all entry criteria will proceed with treatment, visits, and assessments according to *Table 8.2, Schedule of Events*. See *Section 8.5, Study Procedures and Assessments* for more information on individual clinical and research assessments. Participants who do not meet eligibility criteria will be permitted to rescreen once. In addition, participants who cannot complete visits 4 (Day 25) and 5 (Day 26) within 12 weeks after the participant's Visit 1 (Day 0) may rescreen and start the study over, if deemed appropriate by the investigator. The participant must be off tofacitinib for at least one month prior to the new baseline phototesting and biopsy.

8.3. Unscheduled Visits

The investigator may schedule visits in addition to those listed in *Table 8.2, Schedule of Events* in order to conduct evaluations or assessments required to protect the well-being of the participant. If disease activity increases or other concerns arise between regularly scheduled visits, participants should be instructed to contact study personnel and may be asked to return to the study site for an "unscheduled" visit.

8.4. Early Termination Visits

An Early Termination Visit should be requested for participants who withdraw from the study prior to Visit 4 (Day 25). See *Table 8.2, Schedule of Events*, for more information about the assessments that should be conducted at an Early Termination Visit.

8.5. Study Procedures and Assessments

8.5.1. Study Drug

- Study drug will be dispensed to eligible participants at Visit 2 (Day 1). Dosing will begin on day 2 and end on day 26 prior to the erythema assessment and biopsy at Visit 5 (Day 26).
- Study drug compliance will be evaluated at Visit 3 (Day 14).
- Study drug compliance will be evaluated at Visit 4 (Day 25) prior to phototesting.
- Pill bottles will be collected, and remaining pills will be counted at Visit 5 (Day 26).

8.5.2. General Assessments

- **Informed Consent**
- **Demographics:** Participants should provide demographic information. In particular, race and ethnicity should be self-identified.
- **Medical History:** Medical history will be performed as part of screening activities and standard medical care. The medical history assessment will include current illnesses/conditions and past medical history.
- **Concomitant Medications:** A current list of prescription and over-the-counter medications, supplements, and treatments for CLE and SLE will be obtained. Assessment of eligibility should include a review of permitted and prohibited medications. The medication, dose, frequency, route, start date, stop date, and indication will be captured in the electronic case report form (eCRF). Medications taken 30 days prior to screening through study completion or termination should be reported.
- **Eligibility Review:** All entry criteria should be reviewed, and eligibility confirmed prior to scheduling Visit 1 (Day 0) and again at Visit 1 (Day 0) before drawing blood or phototesting (UVB exposure).

8.5.3. Clinical Assessments

- **EULAR/ACR Lupus 2019 [23]:** Screening only.
- **CLASI [24]:** This is a validated instrument for evaluating skin inflammation and damage.
- **SLEDAI-2K:** This is a validated instrument for evaluating SLE disease activity. Each component has a weighted point value which can sum up to 105. Conditions that are ongoing, recurrent, or new should be assessed consistently in relation to a participant's lupus disease activity. A score ≥ 6 is indicative of active disease.
- **Physical Examination:** A comprehensive physical examination will be performed at each clinic visit where the CLASI and/or SLEDAI 2K are indicated. See Table 8.2, *Schedule of Events*, for more detail.
- **Height, Weight, and Vital signs:** Height and weight will only be collected at Screening. Vital signs will include pulse, blood pressure, and temperature (C°). Vital signs should be obtained with the participant in a seated position prior to taking samples for laboratory testing at applicable study visits.
- **Fitzpatrick Scale Assessment[25]**
- **Adverse Event Monitoring**

8.5.4. Clinical Laboratory Assessments

Blood and urine for the clinical laboratory assessments listed below will be collected per Table 8.2, *Schedule of Events*. The results will be evaluated for safety by the site investigator. Abnormal tests that meet grading and reporting criteria will be reported as adverse events (See Section 12.3.1, *Grading Criteria*).

- **Hematology:** complete blood count (CBC) including hemoglobin, hematocrit, white cell count, absolute neutrophil count, absolute lymphocyte count, and platelet count; and erythrocyte sedimentation rate (ESR).
- **Blood Chemistry:** including lipids (triglycerides and cholesterol), ALT, AST, bilirubin, creatinine, eGFR, C3, C4.
- **Urinalysis:** including protein: creatinine ratio, RBCs, and WBCs.
- **Serum immunoglobulins:** including anti-ds DNA.
- **Infectious Disease Testing** (Screening only): including HIV antigen/antibody or NAT, IGRA or PPD, hepatitis B surface antigen, hepatitis B core antibody, and hepatitis C virus (HCV) antibody with HCV RNA (PCR) if antibody positive
- **Pregnancy Testing:** serum pregnancy test (Screening), urine pregnancy test (Visit 4 (Day 25) or Early Termination Visit).

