4.2. Inclusion Criteria

Individuals must meet all of the following inclusion criteria to be eligible for enrollment in the study:

1. Cutaneous lupus erythematosus based upon all of the following:
 - a. a clinical diagnosis made by a rheumatologist or dermatologist of one of the following: acute cutaneous lupus erythematosus, subacute cutaneous lupus, or chronic cutaneous lupus erythematosus;
 - b. active skin disease within 5 years prior to screening.Participants may have concomitant SLE.
2. SLEDAI-2K score ≤ 4 (clinical criteria only, excludes all laboratory criteria) for all participants regardless of whether they have concomitant SLE.
3. If taking oral corticosteroids, the dose must be ≤ 10 mg daily of prednisone (or equivalent), stable dose for at least 4 weeks, and not anticipated to change over the course of the study.
4. If taking oral anti-malarial medications, the dose(s) must be ≤ 100 mg daily for quinacrine or/and ≤ 400 mg daily for hydroxychloroquine, stable for at least 6 months, and not anticipated to change over the course of the study.
5. If taking oral or subcutaneous methotrexate, the dose must be ≤ 25 mg weekly, stable for at least 4 weeks, and not anticipated to change over the course of the study.
6. If taking oral leflunomide, the dose must be ≤ 20 mg daily, stable for at least 4 weeks, and not anticipated to change over the course of the study.
7. If taking oral mycophenolate mofetil (MMF) or mycophenolic acid, the dose must be equivalent to ≤ 3000 mg of MMF daily, stable for at least 4 weeks, and not anticipated to change over the course of the study.
8. Adults 18 to 65 years of age at screening.

9. All participants and/or their sexual partners who engage in sexual activity that could lead to pregnancy must be willing to use complete abstinence or an FDA-regulated form of contraception for the duration of the study and for at least one month after discontinuation of study drug to prevent pregnancy. Highly effective birth control methods include, but are not limited to, hormonal contraception, an intrauterine device, or surgical options. Periodic abstinence and withdrawal are not acceptable methods of birth control.

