10. History of keloid scarring.
11. History of any lymphoproliferative disorder or other malignancy with the exception of successfully treated or excised basal cell or squamous cell skin cancer or cervical cancer in situ.
12. Other autoimmune diseases likely to require immunosuppression.
13. Any of the following lab results at screening:
 - a. Hemoglobin <9.5 g/dL
 - b. White Blood Cell count $<3.5 \times 10^9$ /L

- c. Absolute Neutrophil count $<1.2 \times 10^9/L$
- d. Platelet count $<120 \times 10^9/L$
- e. Absolute Lymphocyte count $<0.75 \times 10^9/L$
- f. Alanine Aminotransferase (ALT) or Aspartate Aminotransferase (AST) $> 1.5 \times$ the upper limit of normal (ULN)
- g. Total bilirubin $>$ ULN
- h. Estimated glomerular filtration rate [GFR] $<60mL/min/1.73 m^2$
- i. Triglycerides $\geq 300 \text{ mg/dL}$ (fasting not required)
- j. Total Cholesterol $\geq 240 \text{ mg/dL}$ (fasting not required).

14. Major surgery $<$ 8 weeks prior to Visit 1 (Day 0).

15. Hospitalized for serious infection $<$ 4 weeks prior to Visit 1 (Day 0).

16. Chronic infections other than chronic or intermittent uncomplicated urinary tract infections (including but not limited to tuberculosis (TB), chronic pyelonephritis, osteomyelitis).

17. Presumed or documented COVID-19 infection within 30 days prior to Visit 1 (Day 0).

18. Recent (within one month prior to screening) close contact with a person who has active TB infection.

19. History of untreated active or latent TB infection.

20. History of incompletely treated active or latent TB infection unless at least one month of treatment has been completed prior to screening.

21. Positive Interferon-Gamma Release Assay (IGRA) or positive purified protein derivative tuberculin skin test (PPD) ($> 5\text{mm}$ induration) at screening.

22. An indeterminate IGRA at screening unless followed by a subsequent negative IGRA or negative PPD.

23. History of human immunodeficiency virus (HIV).

24. A positive test for HIV antigen/antibody or nucleic acid test (NAT) at screening.

25. History of a hepatitis B infection.

26. A positive test for hepatitis B surface antigen or hepatitis B core antibody at screening.

27. History of a hepatitis C infection.

28. A positive test for hepatitis C antibody (regardless of whether hepatitis C RNA levels are undetectable) at screening.

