29. History of recurrent (more than one episode) herpes zoster, one or more episodes of any of the following: herpes zoster ophthalmicus, or disseminated herpes zoster, or disseminated herpes simplex.

30. Current, recent ($<$ 4 weeks prior to Visit 1 (Day 0)) or chronic use of antibiotic medication, except for suppression of chronic/recurrent urinary tract infection, which is allowed.

31. Simultaneous use of more than one of the following: leflunomide, methotrexate and MMF.

32. Any of the following active medications (oral or parenteral): cyclosporine, voclosporin, cyclophosphamide, tacrolimus, rituximab or other anti-CD20s, or any other investigational or marketed biologic with immunomodulatory properties within a year prior to Visit 1 (Day 0).

33. Any of the following medications (oral or parenteral): azathioprine or belimumab within 3 months prior to Visit 1 (Day 0).

34. Any prior treatment with cell-depleting therapies other than anti-CD20s including but not limited to CAMPATH, anti-CD4, anti-CD5, anti-CD3, anti-CD19 products.

35. Intravenous or intramuscular corticosteroids within 2 weeks prior to Visit 1 (Day 0).

36. Treatment with any investigational agent \leq 4 weeks or \leq 5 half-lives of the investigational drug prior to Visit 1 (Day 0), whichever is longer.

37. Treatment with more than one dose of ketoconazole within one week of screening.

38. Any prior treatment with chlorambucil, bone marrow transplantation, or total lymphoid irradiation.
39. Vaccinated or exposed by close contact, e.g., within a household, to a live/attenuated vaccine \leq 6 weeks prior to Visit 1 (Day 0); or is expected to be vaccinated or to have household exposure to these vaccines during treatment or during the 6 weeks following discontinuation of study medication.
40. Received a non-live vaccine \leq 2 weeks prior to initiation of study drug, or unwillingness of a participant to delay non-live vaccination until 1 month after completion of study therapy.
41. Pregnant or breastfeeding females.
42. History of alcohol or substance abuse, unless in full remission for greater than 6 months prior to first dose of study drug.

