- Strong CYP3A4 inhibitors increase exposure to tofacitinib. Participants taking ketoconazole are excluded from this study.

2. Co-administration with biologic DMARDs or potent immunosuppressive drugs such as azathioprine or cyclosporine is not recommended.

3. Pregnancy, Lactation, and Reproductive potential:

- Available data in pregnant women are insufficient to establish a drug associated risk of major birth defects, miscarriage or adverse maternal or fetal outcomes. Feticidal and teratogenic effects were noted in animal reproduction studies.

- There are no data on the presence of tofacitinib in human milk, the effects on a breastfed infant, or the effects on milk production. Tofacitinib is present in the milk of lactating rats; it is likely that the drug will be present in human milk.
- Pregnancy planning and prevention is recommended for females of reproductive potential and is planned for this study.

4. **Vaccinations:** Avoid use of live vaccines concurrently with tofacitinib. The interval between live vaccinations and initiation of tofacitinib therapy should be in accordance with current vaccination guidelines regarding immunosuppressive agents.

5. **Hepatic impairment:** Tofacitinib has not been studied in individuals with severe hepatic impairment and its use is not recommended. In studies of individuals with moderate hepatic impairment, tofacitinib blood concentration is higher than individuals with normal hepatic function. Higher blood concentrations may increase the risk of some adverse reactions. In addition, the safety and efficacy of tofacitinib have not been studied in patients with positive hepatitis B virus or hepatitis C virus serology.

6. **Renal impairment:** In individuals with moderate or severe renal impairment, tofacitinib blood concentrations are higher than in individuals with normal renal function.

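### No pregnancy test is scheduled between Screening and the first dose of a first course, so the last negative result can be 3 to 32 days old when tofacitinib starts

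*Combined protocol and SAP*

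**What the plan says.** **Tests scheduled.** Section 8.5.4 lists a "serum pregnancy test (Screening), urine pregnancy test (Visit 4 (Day 25) or Early Termination Visit". In Table 8.2 the serum row is marked at Screening only. The urine row is marked at Visit 4, Early Termination and the Restart Visit. Visits 1 and 2 have no mark in either row.

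**Timing.** Section 8.2 says that "laboratory measures to determine participant eligibility will be conducted within a 30-day screening window", and Table 8.1 sets that window at Days -30 to -1. Drug is handed out at Visit 2. Section 8.5.1 says: "Dosing will begin on day 2 and end on day 26".

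**Eligibility.** Exclusion 41 in Section 4.3 reads "Pregnant or breastfeeding females" and names no time point. The laboratory exclusions in item 13 open differently: "Any of the following lab results at screening". Section 8.5.2 requires all entry criteria to be reviewed, with "eligibility confirmed prior to scheduling Visit 1 (Day 0) and again at Visit 1 (Day 0) before drawing blood or phototesting".

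**Protection already in place.** Under inclusion 9 (Section 4.2), participants whose sexual activity could lead to pregnancy, and/or their partners, "must be willing to use complete abstinence or an FDA-regulated form of contraception for the duration of the study" and for at least a month after stopping drug. Pregnancy requires permanent discontinuation (Section 6.5.1), and drug stops at once (Section 12.6).

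**Stated hazard.** On human data, Section 5.1 says: "Available data in pregnant women are insufficient to establish a drug associated risk". It adds that feticidal and teratogenic effects were seen in animals.

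**The concern.** The protocol asks the site to confirm on Day 0 that the participant is not pregnant, but the only laboratory evidence is the screening test. Item 13 does not have this problem, because its wording lets a screening value settle the matter. Exclusion 41 has no such limit, and pregnancy status can change within 30 days.

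Two groups could pass the Visit 1 review while pregnant: those who conceive after the screening test, and those who conceived too shortly before it for the test to detect. They would go through phototesting and biopsies and then start the drug, with nothing scheduled to detect the pregnancy until Visit 4.

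This is a matter of participant safety, not of inference. Section 5.5 says participants gain no direct benefit, so a reducible fetal exposure is hard to justify.

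**Working it through.** The documents state no figure for the age of the pregnancy test, so there is none to reproduce. The check is day arithmetic, with Day 0 counted as a study day.

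**Inputs**
- Screening test day *d*: -30 to -1 (Table 8.1).
- First dose: Day 2 (Sections 3.1 and 8.5.1).
- Visit 4: target Day 25, window Days 21 to 29 (Table 8.1).
- Replacements: up to 3 for safety or tolerability and up to 18 for other reasons (Section 11.3), with a target of 10 completers.

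**1. Age of the last negative test at first dose: 2 − *d***

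| Last test before dosing | Calculation | Age at first dose |
|---|---|---|
| Screening, Day -30 (as planned) | 2 − (−30) | 32 days |
| Screening, Day -1 (as planned) | 2 − (−1) | 3 days |
| Added at Visit 1, Day 0 | 2 − 0 | 2 days |
| Added at Visit 2, Day 1 | 2 − 1 | 1 day |

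**2. Doses taken before the next scheduled test.** With one dose each morning from Day 2, and the dose on the day of Visit 4 counted:
- Visit 4 on Day 25: 25 − 2 + 1 = 24 doses.
- Visit 4 on Day 29: 29 − 2 + 1 = 28 doses.

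**3. Gap between the screening test and the Visit 4 test**
- On target Day 25: 25 − (−1) = 26 days to 25 − (−30) = 55 days.
- At the late edge of the window, Day 29: 30 to 59 days.

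**4. Comparison with a restarted course.** At the Restart Visit, Table 8.2 marks a urine pregnancy test. Footnote H has the laboratory work done urgently, drug dispensed once eligibility is reconfirmed, and the first dose taken the next day. The result is therefore about 1 day old when a second course starts, against 3 to 32 days for a first course.

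**5. Ceiling on extra tests.** 10 + 3 + 18 = 31 participants, if every permitted replacement is used and all can become pregnant. Anyone who rescreens and starts over under Section 8.2 would add to this. Such a person also repeats the screening test, and the same 3 to 32 days then applies to the new start.

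**The case against.** The strongest reply is that this is a design choice and breaks no rule in the documents. They set no maximum age for a pregnancy test, and the serum test follows the 30-day rule in Section 8.2. Section 5.1 answers the reproductive risk with planning and prevention, not repeat testing. Contraception is required, periodic abstinence and withdrawal do not count, and a participant who suspects pregnancy has a route to stop drug before Visit 4. All of this is correct and makes the residual risk smaller. However, willingness to use contraception does not show current status, and the stopping rule acts only once a pregnancy is recognised.

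Four narrower objections:
- **Other exclusions also lack a time point** (4, 10 and 12, for example), and none of them has a Day 0 test. This is fair against a purely textual argument. But those are histories or long-standing conditions, whereas pregnancy can begin within the screening window and a simple test can detect it.
- **The Restart Visit test is the counterpart of the screening test, not of a Day 0 re-test.** This is also fair. The comparison still shows that a urine test the day before dosing is workable in this trial.
- **Section 5.4 names no pregnancy-specific risk of UVB exposure or biopsy.** This stands. The documented hazard is the drug, so a test at Visit 2 before dispensing would address it as well as one at Visit 1.
- **32 days is the permitted extreme.** This stands too. The documents do not say how close to Day 0 sites will screen.

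**Conclusion.** The point holds. For a first course, no pregnancy test is scheduled between Screening and the Day 2 dose, and the last negative result may be 3 to 32 days old. That range assumes that visits run to plan and that sites do no testing beyond the schedule.

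The number of exposures this could allow cannot be estimated. The documents give neither a conception rate nor the number of participants who can become pregnant. With about 10 to 31 participants on contraception it is likely to be small. The case for change rests on the seriousness of the animal findings, the lack of direct benefit and the low cost of the remedy.

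There is no effect on Type I error, power or the target of 10 completers. A participant who tests positive at Visit 1 would be ineligible, and enrolment would simply continue. A pregnancy found during treatment ends dosing, and the participant may be replaced under Section 11.3 if the second phototest and biopsy are not completed.

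An added test would find pregnancies detectable by that day. It would not find one too recent to detect, and it would not prevent exposure after a later conception.

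**What to change.** Add a urine pregnancy test at Visit 1, with a negative result required before phototesting, for every participant who can become pregnant. Visit 2 before dispensing is an equally sound place for the drug risk and gives the fresher result. Visit 1 has the advantage of supporting the eligibility confirmation that Section 8.5.2 already requires there, and of sparing an ineligible participant the procedures.

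Two edits are needed:
- **Table 8.2:** mark the urine pregnancy row at Visit 1 (or Visit 2).
- **Section 8.5.4:** list serum at Screening, and urine at Visit 1 before phototesting, Visit 4, the Restart Visit and Early Termination. This also brings the text into line with the Restart Visit test that the table already shows.

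The cost is one urine test per participant who can become pregnant, at an existing visit and of a kind the trial already uses. The ceiling is about 31 participants, plus any who start over. No new visit or blood draw is needed.

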8.5.5. Research Assessments

- **Blood for Serum Biomarkers** will be drawn at Visit 1 (Day 0) and Visit 4 (Day 25).
- **Blood for Cellular and Proteomic studies** will be drawn at Visit 1 (Day 0) and Visit 4 (Day 25).
- **UVB Exposure:**
 - A UV Lamp (Ultralite Enterprises Model 36P10A 10-UNV or equivalent device) will be identified by model name and number, and manufacturer at each site. The same device will be used for all phototesting at each site. The UVB dose, based upon the distance from the UV lamp to the participant, will be determined using dedicated photometer and probe prior to each use.

Phototesting will occur at the study site. A photo-barrier template will be placed on non-lesional skin of the participant's exposed lower back/buttock. The template will be placed on the right lower back/buttock for the phototest on Visit 1 (Day 0) and on the left lower back/buttock for the Visit 4 (Day 25) test. UV irradiation will be applied to the template area via a UV Lamp (Ultralite Enterprises Model 36P10A 10-UNV or equivalent device), and every 40 seconds a single template square of the barrier will be covered until all 8 template squares have been covered (i.e., total exposure ranges from 10-80 mJ/cm²).

Before initiating phototesting at Visit 4 (Day 25), the participant should meet all the following criteria:

- The participant must have completed at least 21 days of IP dosing.
 - For individuals whose Visit 4 (Day 25) has been delayed (See Section 8.1.1, *Exception to Visit Windows*), the 21 days starts from the day IP dosing is resumed.
- The participant must confirm that no IP doses have been missed in the prior 7 days. Dosing will be tracked on a paper patient diary and in the EDC (Electronic Data Capture) system.
- The participant must have taken at least 84% of expected daily doses from the day of the first IP dose. Compliance is based on a pill count conducted at Visit 4 (Day 25).

- For individuals whose Visit 4 (Day 25) has been delayed (See Section 8.1.1, *Exception to Visit Window Rules*), compliance should be computed from the day IP dosing is resumed.

If a participant fails to bring the IP pill bottle(s) back at Visit 4 (Day 25), UVB exposure may proceed during this visit. However, site personnel must confirm at least 84% compliance via a visual pill count prior to the erythema assessment and biopsy at Visit 5 (Day 26). If 84% compliance is not achieved, participant may resume IP dosing. Once the participant has completed appropriate IP dosing, the UVB exposure will be conducted on a site on the lower back, above the original. If the participant does not take the final dose of IP the morning of Visit 5 (Day 26), the erythema assessment and biopsy will still take place, as long as the participant is compliant with their IP dose the 7 days prior to Day 26.

- **Erythema Assessment:**

At Visit 2 (Day 1) and Visit 5 (Day 26), erythema levels for unexposed skin and each template square of the UVB-exposed skin will be quantified using a Chroma Meter (Minolta Model CR-400 or equivalent device). To determine the MED, first compute the average of all the unexposed skin's a* (redness) readings and add 2.5. The lowest exposure with the site's average a* (redness) readings at or above this value is the MED. All skin types (except for Fitzpatrick VI) can be expected to show a response within the planned exposure range[26].

- **Skin Biopsy:** At the indicated time points, 6mm-diameter punch biopsies of nonlesional skin are planned at 3 sites as follows:

1. On Visit 2 (Day 1), 3 biopsy sites on the right buttock include (1) unexposed skin, (2) skin exposed to the 1x MED, and (3) skin exposed to the UVB dose that is 1 step higher than the 1x MED.
2. On Visit 5 (Day 26), 3 biopsy sites on the left buttock will be comparable to those taken on Visit 2 (Day 1), including (1) unexposed skin, (2) skin exposed to the same UVB Dose as the 1x MED from the Visit 2 (Day 1) assessment, and (3) skin exposed to the UVB dose that is 1 step higher than the 1x MED from the Visit 2 (Day 1) assessment. If the 1x MED from the Visit 2 (Day 1) assessment is at the highest UVB dose (80mJ/cm²) or if no erythema is detectable on exposed skin at any dose, then two 4mm biopsies of skin exposed the highest UVB dose will be taken at both Visit 2 (Day 1) and Visit 5 (Day 26).
3. Stitch removal is planned for Visit 3 (Day 14) and Visit 6 (Day 40).

Table 8.2. Schedule of Events

Time Point	Screening	Visit 1	Treatment				Visit 6	Early Termination Visit	Restart Visit ^H	Unscheduled Visit
			Day 1 (20-28hrs after UVB exposure)	Day 14 ^A (Day 10- 15)	Day 25 (Day 21- 29)	Day 26 (20-28hrs after UVB exposure)				
Visit Windows (Days)	(-30 to -1)	Day 0								
Clinical Blood Draw (mL)	20	0	0	0	20	0	0	20	20	20
Research Blood Draw (mL)	0	Up to 50	0	0	Up to 50	0	0	0	0	0
Visit Draw Total (mL) ^C	20	Up to 50	0	0	Up to 70	0	0	20	20	20
Informed Consent	X									
Demographics	X									
Medical History	X									
Concomitant Medications	X	X	X	X	X	X	X	X	X	X
Eligibility Review	X	X							X	
Dispense tofacitinib ^D			X						X	X
Tofacitinib Collection						X		X		
Tofacitinib Count/Confirm Compliance; Review Patient Diary				X	X ^E	X		X		
EULAR/ACR Lupus 2019	X									
SLEDAI-2K	X	X			X			X	X	X
CLASI		X			X			X	X	X
Comprehensive Physical Examination	X	X			X			X	X	X
Fitzpatrick Scale Assessment	X									
Height, Weight, Vital Signs	X	X	X		X	X		X	X	X
Adverse Event monitoring		X	X	X	X	X	X	X	X	X
UVB Exposure		X			X					
Erythema Assessment			X			X				
Skin Biopsy			X			X				
Stitch Removal				X			X	X ^F		

			Treatment							
Time Point	Screening	Visit 1	Visit 2	Visit 3	Visit 4	Visit 5	Visit 6	Early Termination Visit	Restart Visit ^H	Unscheduled Visit
Visit Windows (Days)	(-30 to -1)	Day 0	Day 1 (20-28hrs after UVB exposure)	Day 14 ^A (Day 10-15)	Day 25 (Day 21-29)	Day 26 (20-28hrs after UVB exposure)	Day 40 (Day 36 - 41) ^B			
Complete Blood Count (CBC)	X				X			X	X	X ^G
Erythrocyte sedimentation rate (ESR)	X				X			X	X	X ^G
Lipids	X				X			X	X	X ^G
Chemistries: Liver Enzymes, Bilirubin, Creatinine, eGFR	X				X			X	X	X ^G
C3, C4	X				X			X	X	X ^G
anti-ds DNA	X				X			X	X	X ^G
Urinalysis: Urine Protein/Creatinine	X				X			X	X	X ^G
IGRA or PPD	X									
Hepatitis B surface antigen and core antibody	X									
Hepatitis C antibodies with HCV RNA (PCR) if antibody positive	X									
HIV antigen/antibody or NAT	X									
Serum Pregnancy	X									
Urine Pregnancy					X			X	X	
Blood draw for Biomarkers (Serum)- 10mL		X			X					
Whole blood Proteomic Studies- (40mL at University of Michigan; 10mL at all other study sites)		X			X					

A. Participants who start a new 25-day course of tofacitinib will have a virtual or telephone visit at Day 14 to assess adverse events and concomitant medications.

B. See Section 6.5.1, *Permanent Discontinuation of Investigational Agent*, for more information regarding the Visit 6 (day 40) visit for participants who prematurely discontinue study drug.

C. Lab volumes to not exceed 450 cc every 3 months.

D. See Section 3.1, *Description of Study Design*, for information regarding the timing of IP dosing.

E. See Section 8.5.5, *Research Assessments*, regarding the compliance requirements for phototesting, erythema assessment and biopsy.

F. As needed.

G. Laboratory assessments as relevant to the reason for the Unscheduled visit. These labs must be drawn prior to reinitiating study drug if the participant has had a pause or interruption in IP dosing.

H. In order to reassess entry criteria, all labs will be performed STAT. Once eligibility has been reconfirmed, tofacitinib will be dispensed. The first dose of the new course of tofacitinib will be taken the following day.

9. Mechanistic Assays

Studies on skin biopsies

1. RNA sequencing to identify changes in inflammatory gene expression before and after UV exposure before and after tofacitinib.
2. TUNEL, 8-hydroxyguanosine, and caspase-3 staining to evaluate for cell death before and after UV exposure before and after tofacitinib.
3. Spatial sequencing to evaluate the inflammatory cell populations before and after UV exposure before and after tofacitinib.
4. VgII3 localization in biopsies before and after UV exposure before and after tofacitinib to understand how this regulator of female bias in autoimmunity is modulated in lupus.

Studies on blood

1. Activation of neutrophil NETosis before and after tofacitinib.

10. Biospecimen Storage

1. Formalin Fixed, paraffin-embedded (FFPE) skin biopsies collected as part of this study will be retained for up to 15 years.
2. Plasma from treated participants will be stored for contribution to approved other collaborative projects.
3. Peripheral blood mononuclear cells (PBMCs) from studies left over from neutrophil isolation will be frozen and stored in LN₂ for additional analysis.

11. Criteria for Participant and Study Completion and Premature Study Termination

